### c) Protocol Summary

We plan a test-of-concept of our central hypothesis by conducting a randomized, placebo-controlled, double-blinded, Phase II trial with the following 3 aims:

Aim 1: Test the efficacy of a combination malaria prophylaxis regimen (TMPS-AZ) compared to the standard of care regimen (TMPS) in reducing malaria in HIV-infected pregnant women. The goal is to determine whether the addition of azithromycin has an impact on the proportion with submicroscopic parasitemia at delivery.

Approach: Pregnant women with HIV will be randomized to the intervention (TMPS-AZ) or to usual care (TMPS) with monthly follow-up visits to receive medications. Blood collected at delivery will be tested by PCR to assess for infection with *Plasmodium falciparum*.

Aim 2: Measure the reduction in prevalence of curable bacterial STIs and GBS colonization after 35 weeks gestation (or at delivery) in the intervention and usual care groups. The goal is to measure the impact of monthly AZ prophylaxis on the prevalence of pathogens that are associated with adverse birth outcomes (*Neisseria gonorrhoeae*, *Chlamydia trachomatis*, *Treponema pallidum*, *Streptococcus agalactiae*).

Approach: Participants will have vaginal and anogenital swabs in late pregnancy or at delivery for GC/CT/GBS nucleic acid amplification testing. Blood will be collected simultaneously for syphilis testing.

Aim 3: Determine the fetal/neonatal safety and adherence/tolerability of TMPS-AZ compared to TMPS. The goal is to collect safety, adherence and tolerability data for this novel regimen used in HIV-infected pregnant women.

Approach: Birth outcomes will be captured by chart review and women will fill out a validated questionnaire to assess medication adherence and tolerance at each visit. The first dose of medication at each visit will be given under directly observed therapy.

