#### a) Primary Outcomes

**Aim 1** Proportion of women with *Plasmodium falciparum* peripheral parasitemia by microscopy or PCR.

**Aim 2** Prevalence of a composite STI measure (GC, CT, syphilis infections) will be measured in both groups in late pregnancy (>35 weeks gestation) or at delivery and compared between the two groups.

[figure not shown]
**Aim 3** a) Mean infant birthweight; b) Proportion with adverse birth outcomes, including low infant birthweight (<2500 gm), miscarriage (<28 weeks), preterm delivery (<37 weeks), small for gestational age (SGA), stillbirth (>28 weeks), congenital anomaly at birth, early neonatal mortality (within 7 days); and c) maternal adherence to and tolerance of the prophylactic regimen (vomiting, rash/allergic reactions, dizziness, weakness).

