## **XI. SAMPLE SIZE CONSIDERATIONS**

AIM 1: To test the hypothesis that the addition of AZ to standard preventive therapy in pregnant women with HIV will be associated with a lower proportion of women with peripheral parasitemia detected by microscopy or PCR at delivery, we assumed a 30% prevalence of parasitemia in the TMPS arm based on prior studies and 15% prevalence in the TMPS/AZ arm. A sample size of 134 pregnant women per arm has 80% power at a two-sided significance level of 0.05 using a chi-square.

We will plan for 15% loss to follow up (LFU) and will recruit 154 women per arm (308 women total).

AIM 2: Based on the sample size of 308 evaluable participants at the time of delivery and an expected prevalence of 30% for one or more STIs (CT 20%, GC 5%, syphilis 5%) there will be >80% power at a two-sided significance level of 0.05 to detect a 50% lower STI prevalence in the intervention arm.

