## **XII. DATA ANALYSIS AND MANAGEMENT**

Data management and analysis will be led by the University of Alabama at Birmingham under the supervision of the study PI ([name]).

The primary analysis will be by intention to treat for women who are randomized and receive at least 1 dose of study medication.

The “per protocol” analysis will be performed on women who came to at least one follow up visit following the enrollment visit, reported excellent (>90%) medication adherence, and had outcomes captured (ie – not lost to follow up).

**Statistical Analysis:** Descriptive statistics will be used to compare the study participants between each arm and the primary analysis will be intention-to-treat for the primary outcome of proportion of women with parasitemia. The analysis plan for categorical outcomes is chi-square, Fisher’s exact tests as needed for small sample sizes and we plan to use t-test and Wilcoxon Rank-Sum tests for continuous outcomes. Women will be considered lost to follow up if they do not have a study visit after 35 weeks or at delivery for outcome ascertainment.

For the secondary outcomes, the significance of differences in proportion will be explored using the Pearson’s  $\chi^2$  test or Fisher’s exact test. Multivariable regression modeling will be used to evaluate baseline factors associated with parasitemia if there is imbalance between the arms despite randomization. Potential covariates include age, parity, educational level, monthly income, marital status, history of negative birth outcomes, CD4 count, ART adherence, bed net usage, malaria treatment received and number of study visits. All analyses will be performed in SAS v 9.3.

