# Outcome event: peripheral parasitemia			
# Placebo group event rate: 30%			
# Experimental group event rate: 15%			
# 15% loss to follow up			
# Type 1 error 5% (2-sided)			
# Power 80%			

Registered at Clinical Trials Website ([clinicaltrials.gov](https://clinicaltrials.gov)): NCT03431168

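### Aim 3 lists birth harms as primary outcomes but plans only significance tests for them, so a non-significant result would say little about safety for the rarer harms

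*Combined protocol and SAP*

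**What the plan says.** Section I.c (Protocol Summary) states Aim 3 as a comparison: "Determine the fetal/neonatal safety and adherence/tolerability of TMPS-AZ compared to TMPS". The next sentence is softer: "The goal is to collect safety, adherence and tolerability data for this novel regimen used in HIV-infected pregnant women".

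Section III.a lists the Aim 3 outcomes under Primary Outcomes. Mean birthweight comes first, then "Proportion with adverse birth outcomes, including low infant birthweight", and the list continues with "miscarriage (<28 weeks), preterm delivery (<37 weeks), small for gestational age (SGA), stillbirth (>28 weeks), congenital anomaly at birth" and early neonatal death. That is seven adverse birth outcomes plus birthweight, adherence and tolerance. Appendix A also puts safety and mean birthweight among the primary measures.

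Section XII gives the between-arm methods. For proportions, "The analysis plan for categorical outcomes is chi-square", with Fisher's exact where numbers are small. For birthweight, "we plan to use t-test and Wilcoxon Rank-Sum tests for continuous outcomes". Regression is mentioned only for parasitemia. No risk difference, risk ratio, mean difference, confidence interval or harm margin is planned.

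Section XI sizes the trial for Aim 1 ("A sample size of 134 pregnant women per arm has 80% power at a two-sided significance level of 0.05 using a chi-square") and gives power for Aim 2. It says nothing on Aim 3 and assumes no harm rate.

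**The concern.** For Aims 1 and 2, rejecting no difference supports the stated hypothesis, so a test at least addresses the question. Safety is different. The reader needs to know how large an increase in harm the data still allow, and a p-value above 0.05 does not say. It can arise because the regimen adds no harm or because events are too few to show it.

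The plan gives the reader no means of telling these apart: Section XI is silent on Aim 3 precision and Section XII plans no intervals. This matters most for the rare and serious outcomes (stillbirth, early neonatal death, congenital anomaly) of a combination on which Section II itself says more data are needed.

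**Working it through.** **Inputs.** Two-sided 0.05 and 1:1 allocation (Section XI, Appendix A). Evaluable number per arm: Section XIII gives 268 women, so 134. Taking 15% loss from the 308 recruited gives 308 × 0.85 = 261.8, so about 131. Both are used below. Control-arm harm rates *p* are not in the documents; **the values here are assumptions**.

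**The plan's own figure.** For 30% v 15% with 80% power, the usual two-proportion formula gives 121 per arm without continuity correction and 134 with it. The stated 134 reproduces. It describes parasitemia, not harms.

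**Step 1: power to detect a doubling (chi-square, no continuity correction).** With p̄ the mean of p and 2p,

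power = Φ{ [p − 1.96√(2p̄(1−p̄)/n)] / √([p(1−p) + 2p(1−2p)]/n) }.

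Example, p = 5%, n = 134: (0.05 − 0.0631)/0.0320 = −0.41, so power is 34%.

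**Step 2: what an interval would show if the observed rates were identical.**

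- Risk ratio: upper 95% limit = exp{1.96√(2(1−p)/(np))}. At p = 5%, n = 134: exp(1.96 × 0.5325) = 2.84.
- Risk difference: half-width = 1.96√(2p(1−p)/n). At p = 10%, n = 131: 7.3 points.

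| Assumed control rate | Power for a doubling, n = 131 / 134 | Risk-ratio upper limit, 131 / 134 | Risk-difference half-width in points, 131 / 134 |
|---|---|---|---|
| 2% | 16% / 16% | 5.45 / 5.35 | 3.4 / 3.4 |
| 3% | 21% / 22% | 3.96 / 3.90 | 4.1 / 4.1 |
| 5% | 34% / 34% | 2.87 / 2.84 | 5.3 / 5.2 |
| 10% | 62% / 63% | 2.07 / 2.05 | 7.3 / 7.2 |
| 15% | 83% / 84% | 1.78 / 1.77 | 8.6 / 8.6 |
| 20% | 95% / 95% | 1.62 / 1.61 | 9.7 / 9.6 |

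Fisher's exact test, which the plan uses for small numbers, has less power at 134 per arm: 7% at 2%, 26% at 5% and 58% at 10%.

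**Step 3: the rate above which identical observed rates exclude a doubling.**

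- Risk-ratio scale: p > 1/[1 + (ln 2/1.96)² n/2], which is 10.9% at 131 and 10.7% at 134 (9.4% at 154, with no loss).
- Risk-difference scale (half-width below p): p > 1/[1 + n/(2 × 1.96²)], which is 5.5% at 131 and 5.4% at 134.

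Identical observed rates are only one possible result. If there is truly no effect, the chance that the risk-ratio interval excludes 2 is Φ(ln 2/SE − 1.96), where SE is the standard error of the log risk ratio. At 134 per arm this is 26% at 5%, 47% at 10% and 81% at 20%.

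**Step 4: other outcomes.** With no events among 134 women, the upper limit of the two-sided 95% interval for that arm's rate is 1 − 0.025^(1/134) = 2.7%. For mean birthweight the half-width is 1.96√(2/134) = 0.24 SD, or 96 to 144 g for an assumed SD of 400 to 600 g.

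**Illustration.** Suppose 4 of 131 v 10 of 131 events (hypothetical). Fisher's test gives p = 0.17. The risk ratio is 10/4 = 2.5, with SE of its log √(1/4 − 1/131 + 1/10 − 1/131) = 0.579 and a 95% interval of about 0.80 to 7.8. The planned analysis specifies the p-value; the interval carries the safety information.

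**The case against.** Several objections have force.

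- **A reader might infer that the trial will declare the regimen safe if p exceeds 0.05.** The documents do not support that. No section states such a rule, and Section I.c also describes the goal as collecting data, within a Phase II test of concept. What can be said is that nothing in the plan guards against that reading.
- **A reader might also infer that the trial cannot exclude a doubling of most harms.** That depends on rates the documents do not give. Low birthweight, preterm delivery, small for gestational age or a composite may exceed 11%, where identical observed rates exclude a doubling. On the risk-difference scale about 5.5% is enough.
- **The tests can show harm**, and outcomes defined as proportions and means will presumably be tabulated by arm. True, but arm-level percentages without an interval still leave the remaining uncertainty unstated.
- **A test of difference has a purpose here.** Section II cites studies in which added azithromycin reduced low birthweight and preterm delivery, and Section III.b lists adverse birth outcomes under Aim 1 as well. This supports keeping the tests, but not relying on them alone for Aim 3.
- **Safety has other oversight.** Section IX classes stillbirth, neonatal death and congenital anomaly as serious adverse events, assessed for relatedness and reviewed by the DSMB. No statistical criterion is given, so this does not supply the missing between-arm estimate.

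**Conclusion.** The point holds in limited form. Primary safety outcomes have no planned effect estimate, interval or stated precision, and the tests that are planned cannot show how much harm remains possible.

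For harms with control rates of 2% to 5%, a true doubling would be missed about two times in three or more often (power 16% to 34%). Identical observed rates would leave risk ratios up to about 2.8 to 5.4 inside the 95% interval. By 15% to 20%, power for a doubling is 83% to 95% and identical rates would exclude one, so the concern fades for common outcomes.

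These sizes rest on assumed control rates, 131 to 134 evaluable women per arm and large-sample formulas, which are rough at the lowest rates. The choice between 131 and 134 hardly matters. The choice of scale does: the threshold for excluding a doubling is about 11% for the risk ratio and 5.5% for the risk difference. The plan should be changed, but this does not threaten the Aim 1 or Aim 2 analyses.

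**What to change.** **Section XII.** Make estimation the Aim 3 analysis:

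- For each adverse birth outcome, give the risk difference and risk ratio with 95% confidence intervals, using exact or score intervals where events are rare.
- For birthweight, give the mean difference with its 95% interval.
- Account for clinical site, since randomization is stratified by it (Section V.d).
- Keep the chi-square, Fisher, t and Wilcoxon tests as supportive.
- State that safety conclusions rest on the confidence limit on the harm side, and that a non-significant result will not be described as evidence of safety.

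**Section XI.** Add a short table of expected interval widths over a range of assumed control rates, such as the one above, labelled as assumptions. It should show which increases the trial could and could not exclude.

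**Cost.** A little more programming and a more cautious safety statement. No change to recruitment, visits or data collection.

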### **d) Randomization Method and Masking**

Consenting women will be assigned to one of two prophylaxis groups with a computer generated variable size (2, 4, 6) block randomization sequence prepared in advance by a co-investigator at the University of Alabama at Birmingham. The active and placebo study medication will be indistinguishable in appearance and packaged according to the randomization sequence so that the patient is randomized when she is assigned to the next available individual supply of study medication. The study is double masked; neither the patient nor the clinical staff will be aware of the assigned prophylaxis.

Randomization will be stratified by clinical center to assure balance between the two study groups with respect to anticipated differences among the clinic populations and possible differences in patient management. A unique study ID will be provided to each patient after they are randomized (starting with 5001D for the Douala site, starting at 9001M for the Mutengene site).

The PI and all staff responsible for assessing outcomes (laboratory and clinical) will be blinded to the randomization arm.

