## Appendix A – DESIGN SUMMARY

The PREMISE Trial: A Randomized Clinical Trial to Prevent Malaria and STI in Pregnant Women with HIV			
OBJECTIVE To determine whether or not the addition of Azithromycin (AZ) to standard Cotrimoxazole prophylaxis reduces infection in Cameroon			
ORGANIZATION	SCHEDULED EVALUATIONS/DATA COLLECTION		
Clinical Centers	Mboppi Hospital in Douala, Cameroon Baptist Hospital in Mutengene, Cameroon University of Alabama at Birmingham, US	Pre randomization:	# History, GA, HIV status
Principal Investigator	[name]	Post randomization:	# thick smear, DBS and vaginal swab # visits scheduled q 4 weeks to assess medication adherence and tolerance # sick call visits for fever or complications # thick smear, DBS and vaginal swab # placental collection
DESIGN	Near Term or Delivery:		
Type:	# Phase II, Double masked RCT	OUTCOME MEASURES	
Major Eligibility Criteria:	# HIV-infected # Age $\geq$ 16 # GA 4-28 weeks # Singleton pregnancy	Primary:	# proportion with peripheral parasitemia by PCR or microscopy # composite STI score (GC/CT/syphilis) # safety and mean infant birthweight
Groups:	# Experimental: AZ/Cotrimoxazole # Placebo: Cotrimoxazole	Secondary:	# episodes of symptomatic malaria # proportion with placental parasitemia # composite adverse birth outcomes # maternal anemia (hgb <11 g/dL) # anogenital GBS colonization # proportion with other STI (Mycoplasma genitalium, Trichomonas vaginalis, BV)
Random Allocation:	1:1 allocation	TIMETABLE	
Stratification:	By clinical site	As designed:	# Enrollment: January 2018-July 2019 # Data Collection: January 2018-Dec 2019 # Final Analysis: June 2020
Sample Size:	308 subjects		
Assumptions:			

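### Mean birthweight, an Aim 3 primary outcome, has no designated test and no use of site or baseline covariates; one prespecified linear model would settle the analysis and modestly improve precision

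*Combined protocol and SAP*

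**What the plan says.** Section III.a opens the Aim 3 primary outcomes with "a) Mean infant birthweight; b) Proportion with adverse birth outcomes". Appendix A repeats it in its primary list as "safety and mean infant birthweight".

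The Statistical Analysis paragraph of Section XII covers every continuous outcome with "we plan to use t-test and Wilcoxon Rank-Sum tests for continuous outcomes". It gives no rule for choosing between the two tests and names no effect estimate for birthweight.

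Section V.d states: "Randomization will be stratified by clinical center to assure balance between the two study groups". The reason given is "anticipated differences among the clinic populations and possible differences in patient management". Section XII does not mention site in any analysis.

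The one regression in Section XII concerns parasitemia and is triggered only by observed imbalance between the arms. For that model, "Potential covariates include age, parity, educational level, monthly income, marital status, history of negative birth outcomes", followed by CD4 count, ART adherence, bed net usage, malaria treatment received and number of study visits. Site and gestational age at enrolment are not on the list.

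**The concern.** There are two gaps, both in how one primary outcome will be analysed.

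First, two tests are named without a rule, and they do not target the same quantity. The t-test addresses the difference in means, which is what the outcome is called. The rank-sum test compares rank distributions. The two agree under a pure location shift. They can part company when an effect works through the lower tail, for example through fewer preterm births, and preterm delivery is itself an Aim 3 outcome. With no designated test, the choice could be made after the data are seen.

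Second, the sites were stratified because they were expected to differ, and baseline information is gathered at entry, yet neither enters the birthweight comparison. A linear model that includes them estimates the same mean difference. It can narrow the interval without extra visits, samples or participants.

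**Working it through.** **The plan's own figures.** Section XI gives no SD, target difference or power for birthweight, so there is no birthweight figure to reproduce. Its Aim 1 size does reproduce. For 30% versus 15%, two-sided 0.05 and 80% power, the uncorrected formula gives [1.96·√(2·0.225·0.775) + 0.842·√(0.3·0.7 + 0.15·0.85)]² / 0.15² = 120.5. The continuity correction raises this to 134 per arm, as stated.

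**Inputs**
- Infants per arm: 131 (308 recruited × 0.85 = 262, halved) or 134 (the 268 evaluable women in Section XIII, halved). Both are approximate, because Section XII does not say how miscarriages and stillbirths count.
- Birthweight SD: 500 g, an assumption.
- Share of variance explained by the covariates (R²): 0 to 0.15, an assumption.

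**Formulas.** SE = SD·√(2/n). The half-width is 1.96·SE. The difference detectable with 80% power is (1.96 + 0.842)·SE. Adjustment multiplies each by √(1 − R²). The equivalent gain in sample size is 1/(1 − R²) − 1.

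At n = 131, SE = 500·√(2/131) = 61.8 g. At n = 134, SE = 61.1 g.

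| R² | √(1 − R²) | Half-width, n = 131 / 134 | Detectable difference, n = 131 / 134 | Equivalent gain in women |
|---|---|---|---|---|
| 0 | 1.000 | 121 / 120 g | 173 / 171 g | 0% |
| 0.05 | 0.975 | 118 / 117 g | 169 / 167 g | 5% |
| 0.10 | 0.949 | 115 / 114 g | 164 / 162 g | 11% |
| 0.15 | 0.922 | 112 / 110 g | 160 / 158 g | 18% |

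The percentage gains do not depend on the SD. In grams, the unadjusted detectable difference at n = 134 is 154 g for SD 450 and 188 g for SD 550. If the covariates predict nothing, chance correlation with arm inflates the SE by about √(1/(1 − 5/261)) = 1.01, or roughly 1 g.

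**Site alone.** A simulation used 268 women, sites split 2:1 as in the Section XIII recruitment plan, permuted blocks of 2, 4 and 6 within site, and a within-site SD of 500 g. It ran 8,000 times for type I error and 4,000 times for power against a 150 g difference.

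| Assumed site difference | Type I error, unadjusted / with site | Power for 150 g, unadjusted / with site |
|---|---|---|
| 0 g | 5.1% / 5.1% | 67.7% / 67.6% |
| 100 g | 4.4% / 4.6% | 68.4% / 68.8% |
| 200 g | 4.5% / 4.9% | 68.0% / 68.9% |
| 400 g | 3.7% / 4.9% | 63.9% / 68.8% |

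This pattern is expected. With a 2:1 split, site adds variance (2/3)(1/3)d². For d = 200 g that is 8,889 against 250,000, or 3.4% of the total. For d = 400 g it is 35,556, or 12.5%.

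**Rank-sum test and the mean.** This uses an assumed mixture with 134 per arm: preterm mean 2000 g (SD 500), term mean 3150 g (SD 400), and preterm share 18% versus 8%.
- Equal means. The term mean in the second arm is set to 3025 g, so both arm means are 2943 g (0.18·2000 + 0.82·3150 = 0.08·2000 + 0.92·3025). The t-test rejects 5.0% of the time and the rank-sum test 9.6%.
- Effect only through fewer preterm births. The true difference is 0.10·(3150 − 2000) = 115 g. Power is 38% for the t-test and 26% for the rank-sum test.

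In this mixture the rank-sum test rejects too often when the means are equal and too seldom when they differ.

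**The case against.** The strongest reply is that nothing here is an error. A two-sample t-test after 1:1 randomisation stratified by site is unbiased for the difference in means. A reader might infer from the unused stratum that the planned comparison is invalid. It is not: in the simulation its type I error never rose materially above 5% and fell below it as the site difference grew. This part of the reply stands in full.

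Site by itself is also a weak argument. Up to an assumed 200 g gap, adding it changes power by at most about one percentage point. Only the 400 g case matters, and the documents give no sign of a gap that large. This stands too, and the case for adjustment therefore rests mainly on the prognostic covariates. Their value is assumed: Section XII names age, parity and history of negative birth outcomes for parasitemia, not birthweight. No section says how well any of them, or gestational age at entry, predicts birthweight.

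A reader might also infer that the rank-sum test is assigned to birthweight. It is not. The clause is generic and also serves outcomes such as parasite density, where a rank test is natural, and the name "Mean infant birthweight" points towards the t-test. What remains is that the document does not say so.

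Nor can birthweight be called the only continuous primary outcome. Adherence, in Aim 3(c), may also be analysed on a continuous scale.

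Finally, this is a Phase II test of concept in which birthweight sits under the safety aim and is not powered. How pregnancy losses enter the birthweight mean may matter more than a few grams of precision. That is fair, but it is a separate question and no reason to leave this one open.

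**Conclusion.** The point holds as a low-cost improvement. The plan leaves the birthweight test undesignated and forgoes precision that it could obtain from data already collected.

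At an assumed SD of 500 g, 131 to 134 infants per arm and R² of 0 to 0.15, the half-width shrinks by 0 to about 9 g from a starting value near 121 g. The gain is modest and could be nil. It rests wholly on the assumed SD and R², because the documents supply neither.

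The rank-sum concern is conditional. It matters only if that test is used as the main analysis of a mean, and the 9.6% and 26% figures belong to one assumed mixture. The documents support neither a claim of bias nor a claim that the t-test should be abandoned.

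**What to change.** In Section XII, define the primary birthweight analysis as a linear regression of birthweight on arm, site, parity, age, gestational age at enrolment and history of negative birth outcomes, all fixed before unblinding. Report the adjusted mean difference with its 95% CI. Keep the unadjusted t-test as a supporting analysis and the rank-sum test only as a labelled sensitivity analysis.

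Do not carry the parasitemia covariate list over whole. Number of study visits and malaria treatment received can arise after randomisation, and the Section VII schedule places CD4 count at the term visit. ART adherence and bed net use are also asked about at follow-up visits, so only a value recorded at baseline would qualify. Gestational age at delivery should not replace gestational age at enrolment, because treatment may affect it.

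Gestational age is established for eligibility and listed as pre-randomisation data in Appendix A. The baseline form is not reproduced in the document, so confirm that parity and history of negative birth outcomes are recorded there or in the chart.

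The cost is SAP wording. The one downside is that a simple rule for missing covariate values must be stated in advance. If the covariates turn out to predict nothing, the loss is about 1% of the interval width.
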